Appendix 2 List of figures and tables

Outcomes	Primary objective	Secondary objective	Exploratory objective
Incidence rate of stroke, major bleeding and death in AF patients (exposed/unexposed), overall and in subgroups	✓		
Annual standardized incidence rate and annual prevalence		✓	
Characteristics of AF patients and associated treatments		✓	
OAC treatment patterns		✓	
Comparison of the incidence rate of stroke, major bleeding, death		✓	
Therapeutic management before/after the first stroke occurring after initiation of OAC therapy		✓	
Impact of an OAC switch on the onset of stroke or death		✓	
Comparison of HCRU and associated costs		✓	
Identification of subgroups among patients with similar profile by clustering models			✓

Table 1 Outcomes by study objective

090177e19d84b8dd3\Final\Final On: 22-May-2023 12:29 (GMT)

[figure not shown]

Figure 1. AF study population according to inclusion and non-inclusion criteria

[figure not shown]
[figure not shown]

Figure 2 Time periods analyzed in the comparative analysis of events of interest in patients exposed and not exposed to OAC

Appendix 3 Identification of events of interests: stroke and major bleeding

Title	ICD-10 code
Unspecified, ischemic stroke (including Transient ischemic cerebral (TIC))	I63, I64, G46, G81, G45
Hemorrhagic stroke (including intracranial bleeding)	I60, I61, I62.9, S064, S065, S066
Gastric, duodenal and rectal bleeding	I850, K226, K250, K252, K254, K256, K260, K262, K264, K266, K270, K272, K274, K276, K280, K282, K284, K286, K290, K625, K920, K921, K922
Acute posthemorrhagic anemia	D62
Intraocular bleeding	H356, H431 H450
Otorragia	H922
Hemopericardium	I312
Respiratory bleeding	J942, R04
Haemoperitoneum	K661
Intra articular bleeding	M250
Uterine and vaginal bleeding	N02, N938, N939, N950, R31
Other bleeding	R58, T792

Stroke

Major bleeding

Appendix 4 Identification of medical history and comorbidities

Disease	ICD-10 codes
Coronary arterial disease (CAD)	I21, I22, I24, I25
Sleep disorders	G47
Cancer	C00 to C80, D00 to D09, D37 to D48, Z510, Z511
Malnutrition	E43, E44, E46,
Morbid obesity (BMI>30)	E66
Hospitalisation for anemia	D50, D53
COPD	J44.9
Peripheral arterial disease	I70.0, I70.2, I70.9
Diabetes	E08, E10, E11, E13, E14
Congestive Heart failure	I50.2, I50.3, I50.4

Appendix 5 Identification of treatments and left atrial appendage (LAA) occlusion

Drug- treatments	ATC or CCAM code
Antivitamin K	B01AA
apixaban	B01AF02
rivaroxaban	B01AF01
dabigatran	B01AE07
Selective serotonin reuptake inhibitor antidepressants (SSRIs)	N06AB
Antiarrhythmics	C01BA, C01BB, C01BC, C01BD, C01BG
Non-steroidal anti-inflammatory drugs (NSAIDs)	M01A;
CYP 3A4 cyt P450 inhibitors	B01AC24, C05AE03, C09BB10, C01BD01, J01FA excepté J01FA02
Proton pump inhibitors	A02BC
Systemic azole antifungals	J02AB et J02AC
Anti-platelet agents	B01AC
Medical procedure of cardioversion	DERP004, DERP003
Other anticoagulants	B01AB, B01AE, B01AF, B01AX
Antihypertensives	ATC: C02, C03, C07, C08, C09 (excluding : C02KX01 (not available in France), C03BA08 (not available for outpatient), C03CA01, C07AA07, C07AA12 (not available in France), C07AG02
glucose-lowering drugs	A10BA Metformin, A10BH DPP-IV inhibitors, A10BJ GLP- 1 receptor agonists, A10BX Glinide, A10BF Alpha Glucosidase inhibitors, A10BB Sulfonylurea and the combinations A10BD07, 08, 10 DPP-IV + Metformin and A10BD02 Sulfonylurea + Metformin and A10A insulins
lipid-lowering drugs	Statins: C10AA, C10BA, C10BX; fibrates: C10AB; omega 3 C10AX06; Monoclonal anti-PCSK-9C10AX13 and C10AX14
Beta-blockers	C07A, C07B, C07C, C07D, C07E, C07F
Antivirals, protease inhibitors	J05AE
CCAM code	LAA occlusion
DASF074	Non-English text

Appendix 6 Details on HCRU analysis

Description of HCRU and cost to be described in the analysis

This list of HCRU will be described and associated cost will be calculated.

List of HCRU and cost categories that will be extracted

Hospital stay(s) (private and public), including:

- Hospital admission
- Hospital at home
- Rehabilitation and recuperative care facilities
- Palliative care
- Emergency visit

Non-hospital / ambulatory care:

- Outpatient physician's visits (private practice, home or outpatient)
- Outpatient paramedic visits
- Dispensing of observable drugs (AF drugs and other)

Number and frequency of sickness benefits

Number and frequency of reimbursed transports

HCRU and Costs related to AF

- Hospital care with a diagnosis of AF
- Treatment related to AF
- Lab tests
- Medical procedures
- Medical devices (LPP)
- Transportation following an AF hospitalization
- Sick leave and invalidity up to 7 days after AF hospitalization

Non-English text

Non-English text

Non-English text

Non-English text

Rationale	
Due to the lack of safety data in the population of AF patients unexposed to OAC over a recent period: 2016-2020 and the need to update data on AF exposed to OAC (no new results have been published since 2016), BMS-Pfizer wish to conduct a population-based cohort study in AF patients, that is, the SIFNOS study. This study will also serve as an opportunity to focus on subpopulations most at risk of negative outcomes. From a public health perspective, this study will allow to describe the changes in AF management following the recommendations issued by the HAS in 2018, and thus will provide additional data to optimize the management of patients in routine practice.

Objectives	
Primary objective:
 
 1. To estimate the incidence rate of stroke (ischemic or hemorrhagic), major bleeding and death in both non-valvular AF patients exposed to OAC (VKA or DOAC) and unexposed to OAC, overall and in subgroups of interest: elderly (≥ 80 years old); patients with CAD; frail patients, patients reported with active cancer, patients reported with previous stroke. 
Secondary objectives:

	
 2. To describe the characteristics of non-valvular AF patients exposed and unexposed to OAC; 3. To compare the incidence rate of stroke, major bleeding, and death between those two populations; 4. To estimate the annual incidence and prevalence of patients with non-valvular atrial fibrillation (AF), exposed and unexposed to OAC; 5. To describe the use of oral anticoagulants (OACs) in non-valvular AF patients initiating treatment (AF patients exposed to OAC therapy); 6. To compare Healthcare Resource Utilization (HCRU) and associated costs between patients exposed to apixaban, rivaroxaban, dabigatran, VKA and patients unexposed to OAC; 7. To describe the therapeutic management before/after the first stroke occurring after initiation of OAC exposure.
	
Exploratory objectives:
 
 - To identify subgroups among AF patients with similar profile
Study Design	Observational retrospective cohort study using French national health insurance claims database (SNDS) of non-valvular AF patients (exposed or unexposed to OAC therapy) from 2016 to 2020.
Study Population	
Adult patients with non-valvular atrial fibrillation between 2016 and 2020 (inclusion period), with a 2-year historical period before index date (i.e. AF diagnosis date).
 
Inclusion criteria
 
Patients are included in the study if they meet all the following criteria:
 
 - Age \geq18 years old at index date 
AND
 
 - Have at least one hospital stay with a principal (PD), related (RD) or associated (AD) diagnosis (in PMSI-MSO) of code I48 (Atrial fibrillation of the International Classification of Disease 10th version, ICD-10) 
OR
 
 - Have an active Long-Term Disease (LTD) with ICD-10 code I48 
OR

- Have initiated an OAC (i.e. new users of OAC) for the AF treatment with or without AF diagnosis (PMSI-MSO or LTD), identifying with a validated and published algorithm with a high specificity (c-index 0,93), using a predictive model developed by Billonnet et al. (16).

Exclusion criteria

Patients will be excluded from the study if they meet any exclusion criteria:

- Patients with a valve disease or valve surgery;
- Standard SNDS exclusion criteria (e.g. unicity of identifier not guaranteed, twins, aberrant demographic data, beneficiaries from Mayotte overseas French territory).

Variables

Variables of interest to meet study objectives are:

Primary objectives:

- Clinical events of interest: Stroke (ischemic/hemorrhagic), major bleeding and death;
- Drug exposure: Incident AF patients exposed to VKA, apixaban, rivaroxaban, dabigatran / incident AF patients unexposed to OAC therapy.

Secondary objectives:

- Sociodemographic characteristics: age, sex, complementary universal health care (CMU-c), aid for complementary health care (ACS) for elderly patients, region of patient's residence;
- Medical history and comorbidities (identified algorithmically with hospital diagnoses, active long-term disease, drugs and medical procedures): coronary arterial diseases (CAD), dementia, ischemic or hemorrhagic stroke, congestive Heart failure, peripheral arterial disease, other vascular diseases, sleep disorders, active cancer (within 6 months in the historical period), age adjusted Charlson Cormordity Index (ACCI) adapted to the SNDS data, frail patient identified by Claims-Based Fragility Index (CFI) adapted to the SNDS data, malnutrition, morbid Obesity, anemia, COPD, history of diabetes, patients at risk of falls identified by an algorithm adapted to SNDS data, patients poly-medicated, patient with at least one nursing home entry available;

	
 - Modified risk scores in AF: 1) thromboembolic risk: modified CHA2DS2VASC identified by an algorithm adapted to SNDS data; 2) hemorrhagic risk scores: modified HAS-BLED identified by an algorithm adapted to SNDS data; - Concomitant treatments: beta-blockers, antihypertensives, antiplatelet drugs, other anticoagulants, non-steroidal anti-inflammatory drugs (NSAIDs), oral corticoids, proton pump inhibitors, Selective serotonin reuptake inhibitor antidepressants (SSRIs), systemic azole antifungals, medical procedure of cardioversion, CYP P450 inhibitors, protease inhibitors, antiarrhythmics, glucose-lowering drugs, lipid-lowering drugs, digitalis glycosides, nitrates derivatives. - Annual standardized incidence rate and prevalence of AF, in exposed and unexposed to OAC, every year (2016-2020); - OAC treatment patterns: Line of treatment / regimen, number of lines of treatment (LOT), duration of treatment, time to next treatment; - Healthcare Resource use (HCRU) and associated costs: ambulatory care, hospital care (MCO), rehabilitation care facilities (SSR), Medications.
Data Analysis	
Primary objective
 
In longitudinal analyses, for each AF population (exposed or unexposed to OAC) and subpopulations of interest:
 
The annual incidence rate will be estimated from the occurrence of each of the events of interest, stroke, major bleeding, and death, during patient follow-up. Annual incidence will be defined as the number of events occurring during the follow-up period divided by the number of person-years of follow-up.
 
Secondary objective 2:
 
Patient sociodemographic and clinical characteristics will be analysed through standard descriptive statistics among incident and prevalent AF patients, according to drug exposure (exposed to OAC or unexposed) between 2016 and 2020.
 
Secondary objective 3:
 
In longitudinal analysis, comparison of incidence rate of stroke, major bleeding and death, in AF patients exposed and unexposed to OAC therapy, will be performed using a Cox

regression model adjusted for covariates and with OAC exposure considered as time-dependent variable.

Secondary objective 4:

In cross sectional analyses per calendar year to 2016 to 2020:

- Annual age-standardized incidence rate will be estimated as ratio of number of newly diagnosed non valvular AF patients to the number of individuals at risk in the French population (based on INSEE data) per calendar year (N per 100,000 inhabitants).
- Annual prevalence as ratio of number of diagnosed non valvular AF patients to the number of individuals in the French population (based on INSEE data) per calendar year.

Secondary objective 5:

In longitudinal analysis during the study period, OAC treatment patterns will be described using a treatment sequence analysis, to define lines of treatment (LOT), switches of OAC, concomitant treatments and temporary or permanent discontinuation. A Sunburst for the visualization will be also performed. Persistence rate at 6 and 12 months after initiation of each OAC and any OAC will be estimate with Kaplan-Meier curves.

Secondary objective 6:

In cross-sectional analyses, HCRU (number and rate of patients using each resource by year of follow up) and associated costs (rate per patient per month (PPPM) in Euros) will be compared between AF patients exposed to OAC and unexposed to OAC every year of follow up. Cost analysis will be performed from the health insurance perspective (reimbursed costs).

Milestones	Start of the study: July 2021
	Data access: Third trimester 2023
	Study report: April 2024

5 Amendments

Version Number and Date	Section of the SAP	Amendment	Reason
None	None	None	None

6 Milestones

Milestone	Date
Scientific committee meeting	July 2021
Review of protocol by SC members	July-August 2021
Regulatory submission of the project to HDH	September 22, 2021
CESREES opinion about the project	December 2021
CNIL approval	March 18, 2022
Review of study statistical analysis plan by SC members	July-August, 2022
CNAM – IQVIA- Pfizer/BMS agreement Signature	Second trimester 2023
Data access by CNAM	Third trimester 2023
Data management by IQVIA	July 2023 – August 2023
Analysis by IQVIA	September 2023 – December 2023
Validation of the results and study report redaction	January 2024 – March 2024
Study report delivery and Review of the report by SC members	April 2024

7 Rationale and Background

7.1 Background

Atrial fibrillation (AF) is a heart rhythm disorder caused by abnormal electrical signals from the atria and is characterized by ineffective atrial contraction and irregular heartbeats. AF can occur in three forms: paroxysmal (episodes lasting less than 7 days), persistent or permanent (lasting more than 7 days) and irreversible (1).

Among patients with AF, more than one-third have associated valve disease, characterized by mitral stenosis or valve prosthesis (1). In this case, AF is called "valvular" (2). Conversely, in patients without associated valvular pathology, AF is said to be "non-valvular".

In France, two-thirds of AF patients are 75 years of age and older. The prevalence of AF is about 1% of the general population and increases with age to reach 10% of the population aged 80 years and over. The male/female sex ratio of prevalent cases is 3:2 (3). The absolute number of cases is equivalent between men and women because of the higher life expectancy in women (4).

Several pathophysiological mechanisms, including blood flow stasis, prothrombotic state, and hypercoagulability induced by AF, can lead to stroke (5). Clinical signs may include shortness of breath at rest, fatigue, palpitations, or chest pain. AF accounts for approximately 15% of all strokes (6).

The therapeutic management aims to prevent thromboembolic complications (risk multiplied by 5), in particular the occurrence of ischemic stroke, to reduce symptoms, to prevent recurrence of AF using antiarrhythmic treatment and to improve the quality of life of patients (4). The 2014 Guidelines of the French National Authority for Health recommend initiating an oral anticoagulant (OAC) in AF patients to prevent the risk of stroke in the event of a high thromboembolic risk identified by a CHA2DS2-VASC score greater than or equal to 2. If the score is equal to 1, the initiation is to be discussed according to risk factors. Among the OACs, the antivitamins K (VKA) (warfarin, acenocoumarol – and fluindione until 2017) were considered as the reference drugs until 2017; the direct oral anticoagulant (DOAC) including direct factor Xa inhibitors (rivaroxaban and apixaban) and direct thrombin inhibitor (dabigatran) could be prescribed as an alternative (4). Recommendations concerning the good use of OACs has been updated in 2018 (5). **Since then, DOAC can also be prescribed as a first-line treatment in non-valvular AF (NVAF) patients.**

The main risk associated with the use of OACs is the occurrence of serious bleeding events requiring careful use and regular treatment reevaluation. Among patients with AF, some populations have this risk of bleeding potentially increased, especially the elderly and frail (8,9), or those having dementia (10). The risk is also increased in patients with coronary arterial disease (CAD) due to antithrombotic therapy with dual antiplatelet and OAC (4). In case of contraindication to oral anticoagulation, in particular because of major risk of bleeding, a left atrial appendage (LAA) occlusion may be considered to prevent the risk of thromboembolism (11,12).

In France, two previous studies published by Santé Publique France described the annual rate of adult patients newly treated with OAC for AF using data from the National Health Data System (SNDS), of which the most recent published in 2021 estimates in 2018 a standardized rate of 410/100,000 inhabitants (6,7). To our knowledge, no such recent French epidemiological data specific to AF unexposed to OAC is available.

The use of OACs and the associated risks were evaluated in the NACORA study conducted in 2014 by the National Health Insurance (CNAM) in collaboration with the National Agency for Medicines and Health Products Safety (ANSM), using data from the SNDS. This study assessed in France, the hemorrhagic and thromboembolic risks in AF patients exposed to VKA and DOAC (rivaroxaban and dabigatran only), over a short exposure periods of 6 months and a study period from 2011 to 2012 (13,14).

Pfizer and BMS laboratories conducted the NAXOS study, following the methodology of the NACORA study, published in 2020, for the reassessment of the reimbursement of apixaban on the data from the SNDS. The NAXOS study compared the 1-year risk of occurrence of stroke and systemic embolism (SE) and major bleeding in patients initiating OACs (apixaban, rivaroxaban, dabigatran, and VKAs) between 2014 and 2016 with AF (15).

By contrast, there is no such data in AF patients unexposed to OAC in France.

7.2 Rationale of the Study

This study aims to address the lack of safety data in the population of AF patients unexposed to OAC over a recent period: 2016-2020. It will also serve as an opportunity to update data in the population of exposed patients since no new results have been published since 2016 and to focus on subpopulations most at risk. Furthermore, the study will allow to describe the changes in AF management following the recommendations issued by the HAS in 2018.

7.3 Rationale of the Public Interest

Pfizer and BMS need for scientific research purposes, to use the National Health Data System (SNDS) databases in order to have more recent data and to consider any changes in the management of AF patients during the 2016-2020 period and wish to update the NAXOS study (finalized in 2016 and submitted to the authorities in 2020). Unlike the previous NAXOS study, the SIFNOS study will extend the epidemiological data to all patients having NVAF (exposed or unexposed to OAC). It will provide data of AF patients, on their socio-demographic characteristics, care pathways and healthcare resource utilization and incidence rate of clinical outcomes. The incidence rate of clinical outcomes, stroke, major bleeding and mortality will also be studied in AF subpopulations of interest. This knowledge is intended to provide additional data to optimize the management of patients in routine practice.

8 Objectives

8.1 Primary Objective

1. To estimate the incidence rate of stroke (ischemic or hemorrhagic), major bleeding and death in both non-valvular AF patients exposed to OAC (VKA or DOAC) and unexposed to OAC, overall and in the following subgroups of interest:
 - Elderly (≥ 80 years old)
 - Patients with CAD
 - Frail patients
 - Patients reported with active cancer
 - Patients reported with previous stroke

8.2 Secondary Objectives

2. To describe the characteristics of non-valvular AF patients exposed and unexposed to OAC
3. To compare the incidence rate of stroke, major bleeding, and death between those two populations
4. To estimate the annual incidence and prevalence of patients with non-valvular AF, exposed and unexposed to OAC
5. To describe the use of oral anticoagulants (OACs) in non-valvular AF patients initiating treatment (AF patients exposed to OAC therapy)
6. To compare Healthcare Resource Utilization (HCRU) and associated costs between patients exposed to apixaban, rivaroxaban, dabigatran, VKA and patients unexposed to OACs
7. To describe the therapeutic management before/after the first stroke occurring after initiation of OAC exposure

8.3 Exploratory Objectives

8. To identify subgroups among non-valvular AF patients with similar profile

Note: Throughout the SAP, the term “AF” will be used to refer to the “Non-valvular AF” population.

9 Research Methods

9.1 Study Design

SIFNOS study is an observational retrospective cohort study using French national health insurance claims database (SNDS). A unique extraction of AF patients (exposed or unexposed to OAC therapy) in SNDS data will be used to conduct the study from 2016 to 2020.

9.2 Setting

The study setting is described in the subsections below.

9.2.1 Study Time Periods

The study time period from January 1st, 2014 to December 31st, 2020 represents the entirety of the dataset (i.e. the extraction period).

It includes the following sub-study periods defined below.

9.2.1.1 Inclusion period

Within the extraction period, the inclusion period is from January 1st, 2016 to December 31st, 2019 and to December 31st, 2020 for sensitivity analyses.

9.2.1.2 Index Date

Depending on the date of first evidence of AF over the study period, AF patients will be included at the following dates:

- On 1st January 2016 for **prevalent AF patients** (i.e., patients diagnosed AF during the historical period);
- On the first date of evidence of AF (first date of diagnosis of AF identified either by a LTD or the start date of a hospitalization, or the first date of OAC dispensation) for **incident AF patients**.

A patient will be considered exposed to OAC at the time of his/her inclusion if at least one dispensation of OAC is issued within 30 days after inclusion (including date of inclusion). In such a case, the index date will be the date of the first dispensation of OAC (cf. Appendix 1).

Otherwise, if no dispensation of OAC will be identified within 30 days from inclusion, the index date will be the date of inclusion.

9.2.1.3 Historical period

The historical period is a period of 2 years before the index date in order to distinguish incident and prevalent AF-patients, describe patient's comorbidities, medical history and history of treatments. Consequently, this historical period starts from January 1st, 2014.

9.2.1.4 Follow-up and Censoring

[figure not shown]
The Follow-up period starts at index date and ends on the date of occurrence of one of the following events:

- Death;
- End date of the study fixed to December 31st, 2019 or to December 31st, 2020 for sensitivity analyses;

- Date of the last reimbursement of care recorded in the SNDS (patients with no consumption or reimbursement of care in the 12 months following the date of last consumption).

9.2.2 Study population

Patients with a AF diagnosis will be identified based on a hospitalization with a diagnosis of AF (discharge diagnosis ICD-10 code I48) or with an active Long-Term Disease (LTD) with ICD-10 code I48 during the study (historical or inclusion) period and on an algorithm developed by Billonnet et al. (16) to identify AF outpatients from new users of OACs (VKA, apixaban, rivaroxaban or dabigatran), from January 1st, 2014 to December 31st, 2019, and to December 31st, 2020 for sensitivity analyses (Figure 1).

* Confirmed AF are part of AF diagnosis

Figure 1. Algorithm for the selection of the study population

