3.1.2. Study time periods

Periods and dates of the study

Inclusion period: Patients will be included from January 1st, 2016 to December 31st, 2019 and to December 31st, 2020 in sensitivity analyses.

Note: Given the uncertainty of the impact of the Covid 19 health crisis on the management of AF patients, for all analyses, the 2020 data will be excluded but included in sensitivity analyses.

Index date for the AF population: The index date will correspond to the date of the first diagnosis of AF, identified by the date of the start of LTD or of the index hospital stay (patients newly diagnosed AF during the study period) and if not filled in (i.e. identified by the initiation of an OAC) to the date of initiation of the OAC for OAC new users.

Historical period: A lookback period of 2 years will be considered before the index date in order to distinguish incident and prevalent AF-patients, describe patient's comorbidities, medical history and history of treatments. Consequently, this historical period will start from January 1st, 2014.

Follow-up period Follow-up will start on the index date and end on the date of occurrence of one of the following events: death or the end date of the study (December 31th, 2019 and to December 31st, 2020 in sensitivity analyses, or the date of the last reimbursement of care recorded in the SNDS (patients with no consumption or reimbursement of care in the 12 months following the date of last consumption).

Data extraction period: The data extraction period will start on January 1st, 2014 and end on December 31st, 2020.

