9.2.3 Patient Selection

9.2.3.1 Inclusion Criteria

Patients will be included in the study if they meet the following inclusion criteria:

- Age ≥18 years old at index date

AND

(

- Patients with at least one hospital stay with a principal (PD), related (RD) or associated (AD) diagnosis (in PMSI-MSO) of code I48 (Atrial fibrillation of the International Classification of Disease 10th version, ICD-10) or with an active Long-Term Disease (LTD) with ICD-10 code I48 during the study (historical or inclusion) period

AND/OR

- Patients who are new users of OACs for the AF treatment with or without AF diagnosis (PMSI-MSO or LTD), identifying with a validated and published algorithm with a high specificity (c-index 0,93), using a predictive model developed by Billonnet et al. (16).

)

Description of the algorithm:

The algorithm for identifying patients exposed to OAC indicated for AF will be based on the patients who receive at least one reimbursement of an OAC (VKA, apixaban, rivaroxaban or dabigatran) during the inclusion period, without use of any OAC in the 24 months prior to the first reimbursement date.

Patients reported with at least one orthopedic procedure (osteoarticular or muscular) of the lower limb (including hip/knee replacement) as corresponding to the indication of primary prevention of venous thromboembolic events, during a 6-week period before the first date of OAC delivery will be excluded.

Then, three groups of patients will be identified:

- Confirmed AF are defined as patients with at least one hospital stay with a PD, RD or AD of code I48 or with an active LTD with ICD-10 code I48 or with an electrical cardioversion procedure or radiofrequency ablation before the first date of OAC delivery during the historical period;
- Confirmed DVT/PE are defined as patients hospitalized with a diagnosis of PE (code I26 in any position) or DVT (codes I80 except I80.0, I81, I82 in any position) or with a doppler ultrasound examinations, CT venography, MR venography or pulmonary scintigraphy during a 6-week period before the first date of OAC delivery;
- Unclassified patients in other cases.

Patients with both confirmed AF and DVT/PE will be excluded.

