9.4 Derived Variables

9.4.1 Derived Variables for the Selection of the Study Populations

First, all the variables representing the inclusion criteria will be derived for each patient (Table I).

Table I. Derived variables for the selection of the population – Inclusion criteria

Variable	Definition
Atrial fibrillation diagnosis	
Binary variable (Yes/No)
 
Equals to “Yes” if the patient meets any criterion below:
 
 – Is hospitalized at least once with any discharge diagnosis (i.e., principal, related or associated diagnosis in PMSI-MSO) of atrial fibrillation during the study (historical or inclusion) period 
ICD-10 codes: I48
 
OR
 
 – Is covered by the LTD status for atrial fibrillation at least one day during the study (historical or inclusion) period 
ICD-10 codes: I48
 
Equals to “No” in other cases

Age ≥18 years	
Binary variable (Yes / No)
 
Derived based on the date of birth attributed to the patient after cleaning the data extraction
 
Equals to “Yes” if the absolute difference between the year of index date and the year of birth is upper than or equal to 18 years
 
See also Data Management Plan in section Error! Reference source not found.
 
Equals to “No” in other cases

Second, a validated and published algorithm using a predictive model developed by Billonnet et al. (16) will be applied for the identification of AF indications in outpatients initiating OAC (Table II).

Table II. Derived variables for the selection of the population – Identification of AF outpatients initiating OAC

Variable	Definition
New users of OACs (for AF outpatients)	
Binary variable (Yes/No)
 
Equals to “Yes” if the patient receives at least one reimbursement of an OAC (VKA, apixaban, rivaroxaban or dabigatran) during the inclusion period, without use of any OAC in the 24 months prior the first date of OAC delivery

Variable	Definition
	
ATC codes: B01AA, B01AF02, B01AF01, B01AE07
 
Equals to “No” in other cases

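### The SAP gives two start dates for the OAC-based AF algorithm: from 2014 its 24-month washout cannot be observed, and from 2016 prevalent AF is ascertained unevenly over time

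*SAP*

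**What the plan says.** **Data available.** SAP 9.2.1: "The study time period from January 1st, 2014 to December 31st, 2020 represents the entirety of the dataset". Protocol 3.1.2 agrees: "The data extraction period will start on January 1st, 2014 and end on December 31st, 2020". SAP 9.2.1.1 states that "the inclusion period is from January 1st, 2016 to December 31st, 2019 and to December 31st, 2020 for sensitivity analyses". On the two-year historical period, SAP 9.2.1.3 adds: "Consequently, this historical period starts from January 1st, 2014".

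**Algorithm window, first statement.** SAP 9.2.2 names three routes to AF (an I48 hospital stay, an I48 LTD, and the algorithm applied to new OAC users). It closes with the dates "from January 1st, 2014 to December 31st, 2019, and to December 31st, 2020 for sensitivity analyses".

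**Algorithm window, second statement.** SAP 9.2.3.1 requires an OAC reimbursement "during the inclusion period, without use of any OAC in the 24 months prior to the first reimbursement date". Table II in SAP 9.4.1 repeats this: "during the inclusion period, without use of any OAC in the 24 months prior the first date of OAC delivery".

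**Where it is used.** SAP 9.2.3.3.1 defines prevalent AF by a diagnosis in the historical period and uses that population for objective 4. SAP 9.7.4.3 subtracts prevalent cases from adult residents to obtain the at-risk denominator for incidence. Table XXI lists 2014-2019 as the period for objective 4. SAP 9.7.6 item 3 plans incidence and prevalence without the algorithm-identified patients.

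**The concern.** The algorithm is meant to recognise AF at the moment an OAC is started. If it is run from the first day of the data, no earlier OAC use can be seen, and a person on treatment for years passes the washout at the first refill in the extraction. The indication screens and model predictors are then read at a refill rather than at initiation.

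If it is run only from 2016, that problem goes away and another appears. AF known only through outpatient OAC use can be found when treatment starts in 2016 or later, but not when it has run continuously since before 2016.

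A programmer could follow either statement, and the two give different prevalent populations. Prevalence by OAC status and its trend are at stake. That trend spans the 2018 recommendations, and describing the change in management after them is one of the study's stated aims.

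**Working it through.** **1. The plan's own look-back.** First inclusion date minus 24 months: 1 January 2016 - 24 months = 1 January 2014. This reproduces the stated start of the historical period. The extraction was therefore sized for an algorithm that starts in 2016.

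**2. Washout that can be observed.** For a first delivery on date d, observable washout = min(24, months from 1 January 2014 to d).

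| First delivery | Months observable | Months missing |
|---|---|---|
| 1 Jan 2014 | 0 | 24 |
| 1 Jul 2014 | 6 | 18 |
| 1 Jan 2015 | 12 | 12 |
| 1 Jul 2015 | 18 | 6 |
| 1 Dec 2015 | 23 | 1 |
| 1 Jan 2016 | 24 | 0 |

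A full washout from 1 January 2014 would need OAC data from 1 January 2012.

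**3. Share of the window affected.** 2014-2015 has 365 + 365 = 730 days. 2014-2019 has 6 x 365 + 1 = 2,191 days. 730/2,191 = 33%. Run to the end of 2020, the share is 730/2,557 = 29%. Under 9.2.3.1 and Table II it is 0%.

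**4. Who would be misread on the 9.2.2 dates.**
- The DVT/PE and orthopaedic screens look back 6 weeks before the first delivery (9.2.3.1, Table II). A patient treated for an older DVT/PE and first seen at a 2014 refill escapes them, falls into the unclassified group, and is scored by the model.
- Table III defines initiation of beta-blockers, antiarrhythmics and antihypertensives by 180 days without a fill. In early 2014 those days precede the data, so continuing users count as initiators, which could raise the predicted probability. The 6-week windows for drug use and Holter or echocardiography are also cut short in January 2014, which could lower it. The net direction is not established.

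**5. Illustration of the false-positive share.** SAP 9.2.3.1 gives sensitivity 63% and specificity 95% at the cut-off. With p the share of unclassified users who truly have AF, PPV = 0.63p / (0.63p + 0.05(1 - p)). The documents do not give p; the values here are assumed.
- p = 0.2: 0.126/0.166 = 76%
- p = 0.5: 0.315/0.340 = 93%
- p = 0.8: 0.504/0.514 = 98%

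So 24% down to 2% of those flagged would not have AF. The two operating figures belong to OAC initiation and may not hold at refills, so this range is not an estimate of the error.

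**6. What is missed under 9.2.3.1 and Table II.** Up to the end of 2015, AF can be found by hospital stay or LTD only. From 2016 it can be found by hospital stay, LTD or algorithm. A continuously treated outpatient without an I48 record fails the 24-month washout in every later year and is never found. If patients found from 2016 onward are carried into later years' prevalent counts, algorithm-only cases start from none at 1 January 2016 and accumulate. Part of any rise in OAC-treated prevalence would then come from the rule.

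**7. Bound on the incidence denominator.** SAP 7.1 puts AF at about 1% of the general population and 10% of those aged 80 and over, valvular AF included. Missing every prevalent case would enlarge the at-risk count by about 1% of residents overall (somewhat more among adults only) and by up to 10% of residents in the oldest stratum. Only part of the stock is missed, so the real effect is smaller.

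**The case against.** The strongest reply is that no faulty run is actually planned. The dates in 9.2.2 end a sentence covering all three routes and match the historical-plus-inclusion period named in it. The operational definitions in 9.2.3.1 and Table II both confine the algorithm to the inclusion period. Section 9.2.1.2 lists first OAC dispensation as evidence of AF only for incident patients, and Table I defines an AF diagnosis by I48 stay or LTD alone. This stands to the extent that a reader who infers that the SAP commits to running the algorithm from 2014 goes further than the text. What the text shows is a contradiction. The Table XXI period leans towards 2014 but also fits a hospital/LTD look-back.

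A reader might also infer that long-term OAC users would corrupt the prevalent pool. The documents do not support that. A long-term user who has AF is a true prevalent case, and error arises only from users without AF who are wrongly flagged.

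Nor can the error be sized by setting the stock of treated AF against the yearly flow of new users. Such a figure counts people with AF, valvular AF included, and says nothing about non-AF users who would be misclassified.

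Finally, a reader might conclude that the hospital/LTD-only definition should become the main prevalence series. That is a trade-off. It drops outpatient-only AF, which the study set out to include, and SAP 9.3.1.1 notes that LTD registration is not mandatory, so that series also undercounts.

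**Conclusion.** The SAP contradicts itself on the algorithm window and should be corrected. On the 9.2.2 dates, one third of the window (730 of 2,191 days) cannot support the 24-month rule, and some continuing users without AF could be flagged. On the 9.2.3.1 and Table II dates the washout is complete for everyone, but ascertainment differs before and after 2016. Algorithm-inclusive prevalence is then understated at first and can rise artificially over 2016-2019. The rise assumes that patients found from 2016 are carried forward.

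The effect is mainly on objective 4: prevalence by OAC status and, to a small degree, the at-risk denominator. Its size cannot be computed, because the documents give neither the number of long-term OAC users without AF nor the number of outpatient-only prevalent cases.

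A reader might extend this to the primary incidence rates and the Cox comparison. Those use incident patients, and anyone entering through the algorithm from 2016 has a fully observed washout. One narrow route remains: Table X sets no OAC-free requirement, so a continuing user whose first I48 stay or LTD falls in 2016 or later can enter as incident.

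**What to change.** - In SAP 9.2.2, give the algorithm its own dates: first OAC deliveries from 1 January 2016, in agreement with 9.2.3.1 and Table II. Keep the 2014 start for the hospital and LTD routes only.
- State in 9.2.3.3.1 that algorithm-only patients cannot be classed as prevalent from 2014-2015, and say in Table XXI what 2014-2015 refers to for objective 4.
- Keep the planned main prevalence series, and present the hospital/LTD-only series (9.7.6 item 3) beside it in Table A13. Do not interpret the 2016-2019 trend in algorithm-inclusive, OAC-treated prevalence without it.

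The cost is SAP wording and slightly more reporting, since both series are already planned. The downside is an undercount of outpatient-only prevalent AF, which the report must state. Keeping a 2014 start for the algorithm would instead need OAC data from 1 January 2012, a wider extraction than the protocol describes.
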